#### 4.4.3 Efficacy

Not applicable

#### 4.4.4 Derived Other Variables

#### 4.4.4.1 Age for Demographics

The age of a subject in the study is the calendar age as defined in the protocol.

#### 4.4.4.2 Duration of a Subject in the Trial

The duration of a subject in the study is computed as follows:

Maximum (date of last visit, date of termination) – (date of visit 1 of that subject) +1.

#### 4.4.4.3 **Duration of the Study**

The duration of the study is computed in days as follows:

Maximum of all subjects (date of last visit, date of termination) – minimum for all subjects (date of Visit 1) +1.

## 5 Statistical Methods and Determination of Sample Size

The statistical analyses will be performed under the responsibility of the Sponsor's Biostatistics platform using SAS® Version 9.4 software or later.

The results of the statistical analysis will be available in the final clinical study report (CSR).

For descriptive purposes, the following statistics will be presented:

Table 5.1: Descriptive statistics produced

Baseline	Categorical data	Number of subjects.	
characteristics and		Percentage of subjects.	
follow-up description	Continuous data	Mean, standard deviation, quartiles, minimum, and maximum.	
Clinical safety results	Categorical data	Solicited: Number and percentage (95% CIs) of subjects.	
		Unsolicited: Number and percentage (95% CIs) of subjects, and number of events.	
Immunogenicity results	Categorical data (seroresponse, ≥4-fold rise, cutoff)	Number and percentage (95% CIs) of subjects.	
	Continuous data	Log10: Mean and standard deviation.	
	(titer / data)	Anti-Log10 (work on Log10 distribution, and anti-Log10 applied): Geometric mean, 95% CI of the geometric mean, quartiles, minimum, and maximum.	
		Graphical representation by Reverse Cumulative Distribution Curve (RCDC).	

The CI for the single proportion will be calculated using the exact binomial method (Clopper-Pearson method, quoted by Newcombe (6), i.e., using the inverse of the beta integral with SAS®.

For immunogenicity results, assuming that Log10 transformation of the titers / data follows a normal distribution, at first, the mean and the 95% CI will be calculated on Log10 (titers / data) using the usual calculation for normal distribution (using Student's t distribution with n-1 degree of freedom), then antilog transformations will be applied to the results of calculations, in order to provide geometric means (GMs) and their 95% CI.

#### 5.1 Statistical Methods

#### 5.1.1 Hypotheses and Statistical Methods for Trial Objectives

No hypotheses will be tested.

For descriptive purposes, the statistics presented on Table 5.1 will be produced.

#### 5.1.1.1 Hypotheses

No hypotheses will be tested.

#### **5.1.1.2** Statistical Methods

## 5.1.1.2.1 Immunogenicity

Descriptive statistics will be provided for the hSBA and rSBA antibody titers against meningococcal serogroups (A, C, Y, and W) and for antibody concentrations against tetanus toxoid contained in MenACYW conjugate vaccine.

In general, categorical variables will be summarized and presented by frequency counts, proportion percentages, and confidence intervals (CIs). The 95% CIs of point estimates will be calculated using the normal approximation for quantitative data and the exact binomial distribution (Clopper-Pearson method) for percentages (6). For geometric mean titers (GMTs), 95% CIs of point estimates will be calculated using normal approximation assuming they are lognormally distributed.

RCDC figures will be provided for the antibody titers against meningococcal serogroups or antibody concentrations against tetanus toxoid contained in MenACYW conjugate vaccine.

In summary, descriptive analyses on A, C, Y, and W serogroups on D0 and D30 (+14 days) will include but not be limited to:

- hSBA and rSBA GMTs and 95% CI
- hSBA and rSBA titer distribution and RCDC
- Percentage of subjects with hSBA titer  $\geq 1.4$  and  $\geq 1.8$  and 95% CI
- Percentage of subjects with rSBA titer  $\geq 1.8$  and  $\geq 1.128$  and 95% CI
- Percentage of subjects with hSBA and rSBA titer ≥4-fold rise from pre-vaccination to post-vaccination, and 95% CI
- Percentage of subjects with hSBA and rSBA vaccine seroresponse rate and 95% CI

In summary, descriptive analyses on anti-tetanus antibody concentrations on D0 and D30 (+14 days) will include but not be limited to:

Geometric mean concentrations (GMCs) and 95% CI

• The percentage of subjects with antibody concentrations to tetanus toxoid  $\geq 0.01$  international units (IU)/mL,  $\geq 0.1$  IU/mL, and  $\geq 1$  IU/mL, and 95% CI

Data from MET54 and MET62 will also be combined and paired to evaluate antibody persistence and overall trend over 3 years. The data to be compared from these two studies will include but not be limited to the following endpoints on D0 (baseline) and D30 in toddlers after having received a single dose of either MenACYW conjugate vaccine or Nimenrix®, as part of study MET54, and on D0 (baseline) and D30 in children after receiving a booster dose of MenACYW, as part of study MET62.

- hSBA and rSBA GMTs and 95% CI
- Percentage of subjects with hSBA titer ≥ 1:4 and ≥ 1:8 and 95% CI
- Percentage of subjects with rSBA titer ≥ 1:8 and ≥ 1:128 and 95% CI
- Geometric mean of anti-tetanus antibody concentrations and 95% CI
- The percentage of subjects with antibody concentrations to tetanus toxoid ≥ 0.01IU/mL and ≥ 0.1 IU/mL

Kinetics curves for hSBA and rSBA GMTs, and tetanus GMC including the 4 time points will also be provided.

#### **5.1.1.2.2** Safety

For this trial, the safety data will be assessed by applying descriptive statistical methods, supplemented by the calculation of CIs to aid interpretation. The exact binomial distribution (Clopper-Pearson method) for proportions will be used in the calculation of the 95% CIs of events.

The frequency and percentage of subjects who had solicited injection site and systemic reactions and their 95% CIs will be provided. These events will be tabulated by type of reactions and intensity for each study group. These events will also be summarized by other categories specified in the endpoints (e.g., time of onset, number of days of occurrence, action taken).

Unsolicited AEs will be collected, coded, and summarized by MedDRA system organ class (SOC) and PT. For each unsolicited AE, the number of subjects with at least one instance of that event will be reported. Unsolicited AEs will also be tabulated by intensity and relatedness of study vaccine and by other categories specified in the endpoints.

Immediate reactions, SAEs, and any event that leads to subject withdrawal from the study will be tabulated separately.

## 5.2 Analysis Sets

Four analysis sets will be used: The Full Analysis Set (FAS), the Full Analysis Set for persistence (FASP), the Per-Protocol Analysis Set (PPAS), and the Safety Analysis Set (SafAS).

#### 5.2.1 Full Analysis Set

#### Full Analysis Set

The FAS is defined as the subset of subjects who received at least 1 dose of the study vaccine and had a valid post-vaccination blood sample result.

## Full Analysis Set for Persistence

The FASP is defined as a subset of subjects who had a valid pre-vaccination blood sample result.

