#### **5.2.5** Populations Used in Analyses

All immunogenicity analyses will be performed on the PPAS. Additional immunogenicity analyses will be performed for exploratory purposes on the FAS. Immune persistence analyses will be performed on the FASP. All safety analyses will be performed on the SafAS. All analyses will be based on the overall study population as well as the type of meningococcal vaccine received in MET54 (subjects who received MenACYW conjugate vaccine and subjects who received Nimenrix® 3 years earlier as toddlers).

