## 5.7 Changes in the Conduct of the Trial or Planned Analyses

The analysis set FASP is added in the SAP. FASP will be used to describe the immune persistence 3 years after primary vaccination with either MenACYW conjugate vaccine or Nimenrix®.

No other significant change occurred during the conduct of the trial not documented in a protocol amendment.

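### Does the full analysis set for persistence need a per-protocol counterpart free of Visit 2 conditions?

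*SAP*

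**What the plan says.** Protocol 12.2.4 places all immunogenicity analyses on the PPAS, with exploratory repeats on the full analysis set (FAS). SAP 5.2.5 keeps both rules, including "All immunogenicity analyses will be performed on the PPAS", and adds a third: "Immune persistence analyses will be performed on the FASP".

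The new set, the FASP, is defined in SAP 5.2.1: "The FASP is defined as a subset of subjects who had a valid pre-vaccination blood sample result". SAP 5.7 declares it as a change from the protocol and gives its purpose: "FASP will be used to describe the immune persistence 3 years after primary vaccination".

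The FAS is limited to children who "received at least 1 dose of the study vaccine and had a valid post-vaccination blood sample result". The PPAS is nested in the FAS. SAP 5.2.2 also removes children for eligibility failures, vaccination errors, prohibited therapy, and a missing, out-of-window or invalid Visit 2 sample.

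SAP 5.1.1.2.1 lists the serogroup summaries at both Day 0 and Day 30. It then adds a linked analysis, "Data from MET54 and MET62 will also be combined and paired to evaluate antibody persistence and overall trend over 3 years", which runs through to the post-booster sample, and "Kinetics curves for hSBA and rSBA GMTs, and tetanus GMC including the 4 time points will also be provided". SAP 5.1.1.1 states that no hypotheses are tested.

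**The concern.** Persistence is the first listed objective, and the set named for it does not screen out children whose Day 0 titre may not reflect three years of waning. Examples are a child given another meningococcal vaccine since MET54, immune globulins in the past 3 months, or antibiotics within 72 hours of the draw. Protocol 5.2.5 excludes all three, and Protocol 6.7 says antibiotics may interfere with the bioassays.

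The obvious cross-check is the Day 0 table on the PPAS. But the PPAS also loses children for events after the Day 0 draw. If the two sets gave different persistence figures, a reader could not say from that pair alone whether deviators or Visit 2 losses were responsible. No defined set removes pre-draw deviators and nothing else.

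Two smaller points add to this. SAP 5.2.5 sends all immunogenicity analyses to the PPAS and persistence to the FASP, without saying which leads where they overlap. The linked MET54-MET62 tables and the kinetics curves serve persistence but include the post-booster sample, so either rule could be read as covering them.

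**Working it through.** The plan has no figure to reproduce here: SAP 5.5 says no sample size calculation was made. The check is a comparison of the set rules, followed by an illustration of size.

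**Set rules at Day 0.** Missing titres are not imputed (SAP 5.3.2), so only children with a valid Day 0 result enter any Day 0 table. Among them:

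| Reason for removal | FASP | FAS | PPAS |
|---|---|---|---|
| Eligibility deviation before the draw | kept | kept | removed |
| Not vaccinated, or no valid Visit 2 result | kept | removed | removed |
| Visit 2 sample out of window | kept | kept | removed |
| Vaccination error or later prohibited therapy | kept | kept | removed |

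The Day 0 denominators are therefore nested. FASP to FAS isolates the second row. FAS to PPAS mixes the other three.

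The interval of 3 years ± 45 days is in the design text (Protocol 5.1.1, SAP 3.1) but not among the numbered inclusion criteria (Protocol 5.2.4). Whether the PPAS applies it depends on how the undefined vaccination window in SAP 5.2.2 is read. The stakes are small: 45/1095 = 4.1% of the interval.

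**Inputs for size.** MET62 group sizes are unknown. I assume 50% to 100% of the MET54 Day 30 groups of 91 and 86 (Protocol 1.2.1.2), so n = 43 to 91. I also assume one to three deviators per group, a titre error of 1.0 to 1.5 log10, a log10 SD of 0.4 to 0.7, and 5% to 10% random loss at Visit 2.

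**Effect of deviators on a FASP percentage.** Shift = k/n for k misplaced children.
- One child: 1/91 = 1.1 points; 1/43 = 2.3 points.
- Three children: 3/91 = 3.3 points; 3/43 = 7.0 points.
- Clopper-Pearson 95% half-width: 9.8 points at 27/91, 11.0 at 43/86, 14.0 at 14/46, 15.6 at 22/43.

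**Effect on a geometric mean titre.** Shift = 10^(k·d/n) − 1; interval limits = 10^(±t·SD/√n) − 1. The tightest case is n = 43 with SD 0.4:
- k = 3, d = +1.5: 10^(4.5/43) − 1 = +27.2%, against an upper limit of +32.8%.
- k = 3, d = −1.5: −21.4%, against a lower limit of −24.7%.

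At each n computed (91, 86, 46, 43), every shift lies inside its interval.

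**FASP-PPAS difference.** Removing k deviators, all at or above 1:8, changes the percentage by (x − k)/(n − k) − x/n.
- n = 91, x = 64, k = 1: 63/90 − 64/91 = −0.3 points.
- n = 86, x = 26, k = 3: 23/83 − 26/86 = −2.5 points.
- n = 46, x = 32, k = 1: 31/45 − 32/46 = −0.7 points.
- n = 43, x = 13, k = 3: 10/40 − 13/43 = −5.2 points.

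Losing m of n at random gives a shift with SD = √[p(1 − p)·n/(n − 1)·(1/(n − m) − 1/n)].
- n = 86: 1.1 points (x = 26, m = 4) to 1.9 points (x = 43, m = 9).
- n = 46: 1.5 points (x = 14, m = 2) to 2.6 points (x = 23, m = 5).

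**The two causes can partly cancel.** Take an extreme case: FASP n = 188 (the planned total), 10 deviators all above a cut-off, and 11 Visit 2 losses all below it (188 − 177, where 177 = 91 + 86 in MET54). That leaves 167 other children, with 60% above the cut-off.
- FASP: (0.6 × 167 + 10)/188 = 58.6%.
- Pre-draw exclusions only: 0.6 × 167/178 = 56.3%.
- PPAS: 60.0%.

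The visible difference of −1.4 points is +2.3 from deviators and −3.7 from Visit 2 losses.

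**The case for a change.** The strongest case for a change is that the SAP created a full analysis set for persistence without the per-protocol partner that the other immunogenicity results have. The factual part stands: no existing set differs from the FASP by pre-draw deviations alone, and the extreme case shows that a small visible gap can hide two larger opposing ones. Adding the set would be cheap, since eligibility deviations must be identified for the PPAS anyway.

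Three things weaken it. First, the FAS tables, if they cover Day 0, separate children not vaccinated or without a valid Visit 2 result. That step holds most of the assumed Visit 2 loss. What stays mixed is pre-draw deviations with out-of-window Visit 2 samples and booster-stage or later deviations. Second, the SAP asks nobody to interpret a difference between sets, so the attribution problem arises only if a reader makes that comparison. Third, calling the two causes similar in size sets a one-sided worst case for deviators beside one standard deviation of random loss, which is not like with like.

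The overlap in SAP 5.2.5 is real but mild. The specific sentence on persistence, repeated in 5.7, is naturally read as governing Objective 1 over the general one. For the linked tables and the curves, the set is simply not named.

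**Conclusion.** No change to the plan is needed. Keeping deviators in an inclusive set, alongside per-protocol Day 0 results, is a fair trade-off. A fifth analysis set would differ from the PPAS at Day 0 only by restoring children dropped for booster-stage or later reasons.

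Deviators are likely to be few: eligibility is checked before the draw (Protocol 5.1.4), and a primary physician who is not the investigator is asked to verify previous vaccines and blood products (Protocol 5.2.5). Under the assumptions above, the largest shift between sets from removing deviators is 5.2 points, at n = 43 and 13/43. The interval half-width there is 14.5 points, so the shift is about a third of it. The group sizes, deviator counts, titre errors and loss rates are all assumed. Many more deviators than three per group would alter the picture, but nothing in the documents suggests that. With no hypotheses tested, no error rate is at stake.

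The unnamed set for the linked tables and curves is missing detail of the kind settled in table shells, with the number of children shown at each time point.

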#### 5.2.2 Per-Protocol Analysis Set

The PPAS is a subset of the FAS. The subjects presenting with at least one of the following relevant protocol deviations will be excluded from the PPAS:

- Subject did not meet all protocol-specified inclusion criteria or met at least one of the protocol-specified exclusion criteria
- Subject did not receive vaccine
- Subject received a vaccine other than the one that he / she was planned to receive
- Preparation and / or administration of vaccine was not done as per-protocol
- Subject did not receive vaccine in the proper time window
- Subject did not provide the post-dose serology sample at Visit 2 in the proper time window or a post-dose serology sample was not drawn
- Subject received a protocol-prohibited therapy / medication / vaccine
- Subject had another protocol deviations that affected the subject's immune response, as determined by the clinical team before locking the database

In addition to the reasons listed above, subjects will also be excluded from the PPAS if their post-vaccination serology sample did not produce a valid test result (i.e., results for all antigens are missing).

In the event of a local or national immunization program with a pandemic influenza vaccine, subjects who receive 1 or more doses of a pandemic influenza vaccine at any time during the study will not be withdrawn from the study.

#### 5.2.3 Safety Analysis Set

The SafAS is defined as those subjects who have received at least one dose of the study vaccine and have any safety data available. All subjects will have their safety analyzed according to the vaccine they actually received.

Safety data recorded for a vaccine received out of the protocol design will be excluded from the analysis (and listed separately).

a for which safety data are scheduled to be collected

## 5.2.4 Other Analysis Sets

## Enrolled subjects

Enrolled subjects are subjects for whom a CRF has been created.

#### **5.2.5** Populations Used in Analyses

All immunogenicity analyses will be performed on the PPAS. Additional immunogenicity analyses will be performed for exploratory purposes on the FAS. Immune persistence analyses will be performed on the FASP. All safety analyses will be performed on the SafAS. All analyses will be based on the overall study population as well as the type of meningococcal vaccine received in MET54 (subjects who received MenACYW conjugate vaccine and subjects who received Nimenrix® 3 years earlier as toddlers).

## 5.3 Handling of Missing Data and Outliers

#### **5.3.1** Safety

No replacement will be done. In all subject listings, partial and missing data will be clearly indicated as missing.

#### **5.3.1.1 Immediate**

For unsolicited non-serious systemic AEs, a missing response to the "Immediate" field is assumed to have occurred after the 30-minute surveillance period and will not be imputed.

For SAEs, missing or partially missing elapsed time from last vaccination recorded if within 24 hours will remain missing and not be imputed. Such SAEs will not be considered as immediate.

## 5.3.1.2 Causality

Missing causality (relationship) for unsolicited non-serious AEs and SAEs will be considered at the time of analysis as related to vaccination.

#### 5.3.1.3 Measurements

Partially missing temperatures will be handled as described in Section 4.4.1.1.1.

#### **5.3.1.4 Intensity**

For solicited reactions, missing intensities will be handled as described in Section 4.4.1.1.1. For unsolicited non-serious AEs, missing intensities will remain missing and will not be imputed.

### **5.3.1.5** Start Date and Stop Date

Missing or partially missing start dates for unsolicited AEs will remain missing and not be imputed. If either the start or stop date is missing or partially missing, the time of onset will be

considered to be missing. Nevertheless unsolicited AEs with missing time of onset will be included in analyses according to the visit collected.

Missing or partially missing stop dates for AEs (solicited reactions and unsolicited AEs) will remain missing and not be imputed.

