9.2.2 Safety Endpoints

The endpoints for the evaluation of safety are:

- Occurrence, nature (Medical Dictionary for Regulatory Activities [MedDRA] preferred term [PT]), duration, intensity, and relationship to vaccination of any unsolicited systemic AEs reported in the 30 minutes after vaccination
- Occurrence, time of onset, number of days of occurrence, intensity, action taken, and whether
 the reaction led to early termination from the study, of solicited (prelisted in the subject's
 diary card [booklet or e-diary] and CRB) injection site reactions occurring up to 7 days after
 vaccination.
- Occurrence, time of onset, number of days of occurrence, intensity, action taken, and whether
 the reaction led to early termination from the study, of solicited (prelisted in the subject's
 diary card [booklet or e-diary] and CRB) systemic reactions occurring up to 7 days after
 vaccination.
- Occurrence, nature (MedDRA PT), time of onset, duration, intensity, action taken, relationship to vaccination (for systemic AEs only), and whether the event led to early termination from the study, of unsolicited AEs up to Visit 2 after vaccination.
- Occurrence, nature (MedDRA PT), time of onset, duration, seriousness criteria, relationship to vaccination, outcome, and whether the SAE led to early termination from the study, of SAEs, including AESIs, throughout the trial.

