9.2.3.3 Unsolicited Adverse Events

In addition to recording solicited reactions, parents / legally acceptable representatives will be instructed to record any other medical events that may occur during the 30-day period after vaccination. Space will be provided in the diary card (booklet or e-diary) for this purpose.

Information on SAEs will be collected and assessed throughout the study, from the time of vaccination until 30 days (+14 days) after vaccination. Any SAE occurring at any time during the study will be reported by the Investigator in the CRB according to the completion instructions provided by the Sponsor; this includes checking the "Serious" box on the AE CRF and completing the appropriate Safety Complementary Information CRFs. All information concerning the SAE is to be reported either as part of the initial reporting or during follow-up reporting if relevant information became available later (e.g., outcome, medical history, results of investigations, copy of hospitalization reports). In case a subject experiences febrile convulsion (neurological event associating fever and seizure), the assessment will be performed according to the "Guideline for definition and collection of cases of febrile convulsion", and this event will be considered an SAE. See Section 10 for further details on SAE reporting.

For each unsolicited AE (whether serious or non-serious), the following information is to be recorded:

- Start and stop dates^a
- Intensity of the event:

For measurable unsolicited AEs that are part of the list of solicited reactions, the size of the AE as well as the temperature for fever will be collected and analyzed based on the corresponding scale used for solicited reactions (see Table 9.1 and Table 9.2).

All other unsolicited AEs will be classified according to the following intensity scale:

• Grade 1: A type of AE that is usually transient and may require only minimal treatment or therapeutic intervention. The event does not generally interfere with usual activities of daily living.

The stop date of all related AEs will be actively solicited. For other events, the investigator will provide the stop date when it becomes available. AEs for which no stop date was obtained during the course of the study will be considered as ongoing at the end of the study.

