#### **4.4.1.2.4** Time of Onset

Time of onset is derived from the start date of the unsolicited non-serious AE provided in the clinical database and the date of last vaccination:

• start date of the unsolicited non-serious AE – date of previous vaccination

The time of onset should be considered as missing only if one or both of the dates are missing or partially missing.

The unsolicited non-serious AEs will be analyzed "Within 30 days", which corresponds to AEs with a time of onset between D0 and D30 days after vaccination or missing. An AE with missing time of onset will be considered to have occurred just after the vaccination indicated by the visit number, so will be included in these tables.

Note: Unsolicited non-serious AE that occurred before vaccination (negative time of onset) or with a time of onset higher than defined above will not be included in analysis, but will be listed separately.

Time of onset will be displayed as follows:

- D0-D3
- D4-D7
- D8-D14
- $\geq$  D15
- Missing

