#### 4.4.1.2.5 **Duration**

Duration is derived from the start and stop dates of the unsolicited non-serious AE provided in the clinical database:

• stop date of unsolicited non-serious AE - start date of unsolicited non-serious AE + 1.

The duration should be considered as missing only if one or both of the start and stop dates of the unsolicited non-serious AE is missing or partially missing.

Duration will be displayed by period as following:

- 1-3 days
- 4-7 days
- 8-14 days
- $\geq 15 \text{ days}$
- Missing

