#### **4.4.1.3.2** Time of Onset

Time of onset will be computed using the same methodology as for unsolicited non-serious AEs described in Section 4.4.1.2.4.

SAEs will be analyzed throughout the study using the following periods:

- Within 30 days
- During the study (i.e., all SAEs that occurred during the study)

An SAE with missing time of onset will be considered to have occurred just after the vaccination indicated by the visit number, so will be included in these tables.

Note: SAEs that occurred before vaccination (negative time of onset) will not be included in analysis, but will be listed separately.

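### The SAP has two incompatible rules for a missing AE time of onset: one ignores the stop date, the other makes onset missing whenever the stop date is missing

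*SAP*

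**What the plan says.** **Derivation section.** SAP 4.4.1.2.4 takes onset as the AE start date minus the date of the previous vaccination. Its missing-data rule is restrictive: "The time of onset should be considered as missing only if one or both of the dates are missing or partially missing". The dates meant are the two in the formula.

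**Missing-data section.** SAP 5.3.1.5 has a different condition, "If either the start or stop date is missing or partially missing, the time of onset will be" treated as missing. It adds that such AEs stay in the analyses according to the visit at which they were collected, and that missing stop dates are not imputed.

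**What follows from a missing onset.** SAP 4.4.1.2.4 states: "An AE with missing time of onset will be considered to have occurred just after the vaccination indicated by the visit number". The AE therefore enters the *Within 30 days* tables. An AE whose known onset is negative or later than D30 is handled in the opposite way. Of the late ones the SAP says that those "with a time of onset higher than defined above will not be included in analysis, but will be listed separately".

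**Related rules.** For duration, SAP 4.4.1.2.5 says: "The duration should be considered as missing only if one or both of the start and stop dates" is missing or partial. For SAEs, SAP 4.4.1.3.2 says: "Time of onset will be computed using the same methodology as for unsolicited non-serious AEs", with a reference back to 4.4.1.2.4. The stop-date footnote in Protocol 9.2.3.3 says: "AEs for which no stop date was obtained during the course of the study will be considered as ongoing at the end of the study".

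**The concern.** For an AE with a complete start date and no stop date, the two rules cannot both apply, because the word *only* in 4.4.1.2.4 excludes the extra condition in 5.3.1.5. The SAP does not rank the sections, and its list of changes (5.7) does not mention the difference. The start/stop condition is exactly what the duration rule needs, so it was probably carried over by mistake. That is an inference; the text does not say so.

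Time of onset is a named component of the unsolicited AE endpoint (Protocol 9.2.2). Two programmers who each follow the SAP could produce different onset tables and different *Within 30 days* counts from the same database. Under 5.3.1.5, whether an AE has resolved, which has no bearing on when it began, would set its onset category and, for starts after D30, decide whether it is counted at all.

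**Working it through.** **The plan's own figure.** There is none to reproduce. The check applies both rules to the same date patterns and then bounds the effect.

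**Inputs.** Onset = start date − vaccination date (SAP 4.4.1.2.4). The analysis window is D0–D30 (same section). Collection runs from D0 to Visit 2, which is D30 to D44 (SAP 3.1; Protocol 5.1.1). There is one vaccination, so a missing onset always points to the D0 dose.

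**The rules side by side.** Hypothetical non-serious unsolicited AEs, vaccination date known:

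| Start | Stop | Under 4.4.1.2.4 | Under 5.3.1.5 |
|---|---|---|---|
| D5 | known | Onset 5, category D4–D7, counted | Same |
| D5 | missing | Onset 5, category D4–D7, counted | Category *Missing*, counted |
| D35 | known | Excluded and listed | Same |
| D35 | missing | Excluded and listed | Category *Missing*, counted as *Within 30 days* |
| Before D0 | missing | Excluded and listed | Category *Missing*, counted as *Within 30 days* |
| Missing | any | Category *Missing*, counted | Same |

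The rules agree when all dates are complete and when the start date is missing. They differ only when the start date is known and the stop date is not. The pre-vaccination row should be rare, since pre-existing conditions are not reported as AEs unless they worsen (Protocol 9.2.1).

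**SAEs.** Their onset is sent to 4.4.1.2.4, so they are affected only if 5.3.1.5 is read as overriding it. A late SAE appears in the *During the study* table either way.

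**Bound from the documents.** Days after D30 as a share of collection days: (44 − 30)/(44 + 1) = 14/45 = 31.1% when Visit 2 is on D44, and 0/31 = 0% when it is on D30. This is a share of days. It is a share of AEs only if the onset rate is constant.

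**One subject.** 1/188 = 0.53 percentage points, taking the planned total as denominator. Results are also given by priming vaccine. With the MET54 D30 hSBA denominators as stand-ins (91 and 86, Protocol 1.2.1.2), one subject is 1/91 = 1.10 or 1/86 = 1.16 points.

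**Illustration under assumptions.** The following are assumed and not in the documents: a constant onset rate; log-normal duration with log SD 0.8 and median 5, 7 or 10 days, rounded up to whole days; and no stop date for any AE still present after Visit 2. The expected share starting after D30 is 2/33 = 6.1% if Visit 2 is uniform over D30–D34, and 7/38 = 18.4% if uniform over D30–D44. By simulation (3,000,000 draws per scenario), as a percentage of all collected AEs:

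| Visit 2 | Median duration | D0–D30 start moved to *Missing* | Start after D30 added to *Within 30 days* |
|---|---|---|---|
| D30–D34 | 5 / 7 / 10 days | 13.8 / 21.0 / 31.0 | 5.2 / 5.6 / 5.9 |
| D30–D44 | 5 / 7 / 10 days | 6.5 / 11.1 / 18.3 | 10.1 / 12.3 / 14.4 |

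If a stop date is later obtained for half of the ongoing AEs, every figure halves. The result depends strongly on these inputs. With a 2-day median and half retrieved, about 1.8% are moved and 1.6% added for D30–D34, and about 0.7% and 2.3% for D30–D44. With a 2-day median and 90% retrieved, all four are below 0.5%.

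**The case against.** The conflict in the text is not in dispute. The case on the other side is that it matters little.

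- **A programmer would follow the derivation section.** It has the formula and the word *only*, and SAE onset is sent there too. That is the likelier outcome, but 5.3.1.5 is the section devoted to missing dates and could fairly be taken as governing. The SAP does not settle it.
- **The consequences are limited.** Both sections keep missing-onset AEs in the analysis. For D0–D30 starts only the onset category changes; incidence, SOC/PT, intensity and relatedness counts do not. No hypothesis is tested. All of this stands, and it is why the impact is moderate.
- **Missing stop dates may be few.** Protocol 9.2.3.3 says stop dates of related AEs are actively solicited, and Protocol 5.1.4 follows related AEs to resolution, stability or chronicity. Protocol 9.2.3.3 also has parents record events over a 30-day period, which could reduce D31–D44 records, although other sections say up to Visit 2. These points stand. The frequency is unknown from the documents, but unrelated AEs have no active stop-date follow-up.
- **The percentages overstate the effect on rates.** They are per AE, while SAP 5.1.1.2.2 counts subjects with at least one instance. A subject already counted for a term adds nothing to that rate. This also stands. The simulated figures only illustrate scale, and the conclusion does not rest on them.

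**Conclusion.** The concern holds. SAP 5.3.1.5 is wrong as written: it conflicts with the SAP's own definition of onset and, if followed, gives incorrect onset categories and incorrect inclusion for ongoing AEs. The error relabels AEs or adds them to a table and hides none; the start dates remain in the database.

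The number of affected AEs cannot be derived from the documents. It depends on how many AEs lack a stop date and how late Visit 2 takes place. The share wrongly added to *Within 30 days* is at most 31% of AEs if the onset rate is constant, and zero if every Visit 2 is on D30. In a descriptive study this is a moderate defect that should be corrected, since the descriptive tables are the whole of the safety result.

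**What to change.** In SAP 5.3.1.5, replace the condition on the start or stop date with one on the start date or vaccination date, and add a sentence saying that a missing stop date makes only the duration missing. This brings 5.3.1.5 into line with 4.4.1.2.4 and 4.4.1.2.5. If the tables are already programmed, confirm that the code derives onset without using the stop date.

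The cost is an edit to one sentence of the SAP and one added sentence. It needs no new data and no change to the conduct of the trial.
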